18. REVISION HISTORY

18.1. Summary of Changes

Protocol Version 2.0 dated 19AUG2021
Replaces: Protocol Version 1.0 dated 08APR2021

The following table describes changes from Version 1.0 (dated 08APR2021) with justifications provided.

Section	Description	Justification
Throughout	Protocol version update. Previously read: V1.0_08APR2021 Now reads: V2.0_18AUG2021	Version control.
Throughout	Minor grammar, content, and style updates.	Minor content updates for clarity/accuracy/style of content.
Table of Contents	Minor content updates.	Minor updates required to reflect revised content.
List of Abbreviations	Minor content updates.	Minor updates required for accuracy and to reflect revised content.
Protocol Summary, 3.3, 4.2.3, 7.2.2.3, 15 (Schedule of Assessments); 17.4	Removed fluorescence-activated cell sorting (FACS) and replaced with flow cytometry.	Clarification of terminology of evaluation.
Protocol Summary, 3.3, 4.2.3, 10.4.4	Modified the exploratory objective and endpoint for assessment of change from Baseline over time in BCVA using the ETDRS method to define the change from Baseline as either gains or losses. Removed the duplicate objective and associated endpoint.	Minor update for accuracy and clarity.
Protocol Summary, 4.2.3	Modified the exploratory endpoint for change in area of ischemia or area of neovascularization from Baseline over time to allow for the assessment to be completed using OCT-A and/or FA.	Clarification of the modality for assessment of the endpoint.
4.1, 7.1.1.1, 7.1.1.2, 7.1.1.3.4, 15	Changed term from indirect ophthalmoscopy to extended ophthalmoscopy.	Administrative clarification.
5.1	[REDACTED]	Updated the window for previous treatment for ease of enrollment.

5.1 and 5.2	
Exclusion Criterion 3, part c was modified and moved to become Inclusion Criterion 7 as follows:
 
Previously read: In addition, the investigator and potential participant are comfortable withholding treatment for DME until there is at least a 10% increase in OCT central subfield thickness with confirmed visual acuity loss (10 letter loss at a single visit or 5 to 9 letters at 2 consecutive visits)
 
Now reads: The investigator and potential participant are comfortable withholding treatment for DME and PDR until protocol-defined treatment criteria are met (see Section 5.4).
	Revised for clarity.
5.2	
Exclusion Criterion 4 was modified to stipulate a treatment window as follows:
 
Previously read: Prior intraocular or periocular steroid injection.
 
Now reads: Prior intraocular or periocular steroid injection within 12 months prior to enrollment and assignment to a randomized treatment.
	Revised to add a window for prior treatment.
5.2	[REDACTED]	Content added based on regulatory feedback.
5.4	Section 5.4 added to detail the threshold for treatment of CI-DME	Content added for clarity on the treatment requirements for the occurrence of CI-DME.
6.2	
Previously read: The disposal of used, partially used, or wasted AKST4290 and/or placebo must be performed in accordance with the institution's drug disposal policy.
 
Now reads: The disposal of used, partially used, or wasted AKST4290 and/or placebo must be performed in accordance with the institution's drug disposal policy or return.
	Clarification of drug return procedures.
7.1.1.2.6	Updated the list of chemistry assessments to include eGFR and removed eGFR from the list of urinalysis assessments.	Correction as eGFR is calculated from serum creatinine and is not a urinalysis assessment.
7.5	The restriction advising participants to avoid alcoholic beverages from 48 hours before study drug administration through the EOS examination was removed.	Text was removed as alcohol is not considered a prohibited drug.
7.5, 17.3, 17.3.1, and 17.3.3	[REDACTED]	Content added based on regulatory feedback.

15, Schedule of Assessments	
Switched the order of assessments for Optional aqueous humor collection and PK blood sample collection for proper footnote ordering.Corrected the footnote letter from “l” to “m” for the rows labeled as “PK blood sample collection (for plasma extraction)” and “Biomarker plasma aliquot”.Clarified footnote “m” to indicate that PK blood samples and samples for biomarker analysis are collected in separate tubes.Removed visual field assessment at Visit 9.	Minor changes for clarity and to remove an assessment that is not required at the End-of-Study visit.
-----------------------------	--	---

## ABBREVIATIONS

**Table 1 List of Abbreviations**

Abbreviation	Definition
AE	Adverse event
AESI	Adverse event of special interest
ALT	Alanine aminotransferase
ASNV	Anterior-segment neovascularization
AST	Aspartate aminotransferase
ATC	Anatomical Therapeutic Chemical
AUC	Area under the curve
BUN	Blood urea nitrogen
CBC	Complete blood count
CI-DME	Center-involved diabetic macular edema
CMT	Central macular thickness
CSR	Clinical Study Report
DILI	Drug-induced liver injury
DM	Diabetes mellitus
DR	Diabetic retinopathy
DRSS	Diabetic Retinopathy Severity Scale
DSMB	Data and Safety Monitoring Board
ECG	Electrocardiogram
eCRF	Electronic case report form
EDC	Electronic data capture
eGFR	Estimated glomerular filtration rate
ENT	Ears, nose, and throat
EOT	End of Treatment
EOS	End of Study
ET	Early Termination
ETDRS	Early Treatment Diabetic Retinopathy Study
FA	Fluorescein angiography
FP-4W	Fundus Photography 4 Wide
FP-7M	Fundus Photography Modified 7 Field
FP	Fundus photography
HbA1c	Hemoglobin A1c
HBV	Hepatitis B virus
HCV	Hepatitis C virus
HIV	Human immunodeficiency virus
ICH	International Council for Harmonisation
IOP	Intraocular pressure
IL	Interleukin
LPLV	Last participant, last visit

Abbreviation	Definition
MedDRA	Medical Dictionary for Regulatory Activities
NPDR	Nonproliferative diabetic retinopathy
OCT-A	Optical coherence tomography angiography
OD	Oculus dexter
OS	Oculus sinister
PDR	Proliferative diabetic retinopathy
PK	Pharmacokinetics
PT	Prothrombin time
PTT	Partial thromboplastin time
QTc	QT interval corrected for heart rate
QTcF	QT interval corrected for heart rate using Fridericia's correction formula
SAE	Serious adverse event
SAP	Statistical Analysis Plan
SD-OCT	Spectral domain optical coherence tomography
SI	Système International
TEAE	Treatment-emergent adverse event
TNF- $\alpha$	Tumor necrosis factor-alpha
UACR	Urine albumin to creatinine ratio
ULN	Upper limit of normal
VF	Visual field
WHODDE	World Health Organization Drug Dictionary Enhanced
WPAI-GH	Workplace Productivity and Activity Impairment General Health

## 1. INTRODUCTION

The purpose of this Statistical Analysis Plan (SAP) is to provide comprehensive and detailed descriptions of the methods and presentation of data analyses proposed for Alkahest, Inc. Protocol AKST4290-231 (A Double-Masked, Placebo-Controlled Study to Evaluate the Efficacy of Oral AKST4290 in Participants with Moderately Severe to Severe Diabetic Retinopathy [CAPRI]). Descriptions of planned analyses are provided in order to avoid post hoc decisions that may affect the interpretation of the statistical analysis. The statistical methods applied in the design and planned analyses of this study are consistent with the International Council for Harmonisation (ICH) guidelines Statistical Principles for Clinical Trials (E9) (1998) and Statistical Principles for Clinical Trials: Addendum: Estimands and Sensitivity Analysis in Clinical Trials (E9[R1]) (2017).

This SAP will be finalized prior to data analysis and before treatment unmasking and database lock to provide comprehensive details of the listings to be presented in the Clinical Study Report (CSR). Any changes between the statistical methods provided in the clinical study protocol and this SAP will be explained herein; any changes or deviations from this SAP relative to the final analysis will be fully documented in the CSR. Minor changes or deviations from the templates for provided listings need not be documented in the CSR.

On 09Dec2021, study investigators were notified the AKST4290-231 study was being terminated. Safety findings related to liver enzyme elevations were discovered in other AKST4290 studies. Out of an abundance of caution, active study participants were required to discontinue study drug and new enrollment was discontinued. Three study participants were randomized and taking study drug at the time of this notification. This SAP has been modified to accommodate the limited number participants enrolled in this prematurely concluded study.

## 2. STUDY OBJECTIVES

### 2.1 Primary Study Objective

The primary objective of this study is to investigate the efficacy of AKST4290.

### 2.2 Secondary Study Objectives

The secondary objectives of this study are:

- To investigate additional measures of efficacy of AKST4290;
- To assess the proportion of participants progressing to (or worsening of) center-involved diabetic macular edema (CI-DME), proliferative diabetic retinopathy (PDR), and/or anterior-segment neovascularization (ASNV);
- To assess the time to event of CI-DME, PDR, and/or ASNV requiring treatment;
- To assess the overall safety of AKST4290;
- To assess the effect of AKST4290 on diabetic kidney disease;

- To evaluate the changes from Baseline in the Workplace Productivity and Activity Impairment General Health (WPAI-GH) questionnaire.

## 2.3 Exploratory Study Objectives

The exploratory objectives of this study are:

- To assess the mean change from Baseline (gain or loss) in BCVA;
- To assess the mean change from Baseline in macular volume and central macular thickness (CMT);
- To assess the proportion of participants with worsening of Diabetic Retinopathy Severity Scale (DRSS) score;
- To assess visual acuity area under the curve (AUC);
- To investigate the impact of AKST4290 when administered at doses of 400 mg b.i.d. on pharmacokinetics (PK), pharmacogenomic, and flow cytometry/complete blood count (CBC) evaluations of interest conducted on blood and plasma samples;
- To evaluate changes from Baseline in optical coherence tomography angiography (OCT-A) (as available at sites);
- To evaluate changes from Baseline in visual field (VF) as assessed by perimetry/microperimetry evaluations (as available at sites);
- To evaluate the change from Baseline over time and the presence of inflammatory biomarkers [REDACTED] n aqueous humor collected from participants who elect to provide these samples.

## 3. INVESTIGATIONAL PLAN

### 3.1 Overall Study Design

This is a Phase 2, double-masked, placebo-controlled multicenter study to evaluate the efficacy of AKST4290 administered at an 800 mg daily dose (400 mg b.i.d.) as compared with placebo over a 24-week dosing period in participants with moderately severe nonproliferative diabetic retinopathy (NPDR) (DRSS Level 47) to severe NPDR (DRSS Level 53) in one eye, and at least mild NPDR (DRSS Level 35) to mild PDR (DRSS Level 61) in the other eye. Both eyes must not have CI-DME, and must have good vision (defined as BCVA of  $\geq$  69 letters using the Early Treatment Diabetic Retinopathy Study [ETDRS] method).

Eligible participants will be enrolled into one of two randomized treatment arms (active and placebo) in a 2:1 fashion of active to placebo. Participants will receive treatment for a total of 24 weeks with either AKST4290 800 mg daily (400 mg b.i.d.) in Arm 1 or placebo (matching tablets) in Arm 2.

[figure not shown]
Once enrolled and allocated to a randomized treatment, all participants will be evaluated monthly throughout the treatment period (ie, at Visits 2, 3, 4, 5, 6, 7, and 8) to assess efficacy and monitor safety for the development of the vision-threatening complications of CI-DME, PDR, and/or ASNV. Participants who develop CI-DME (as confirmed by the central reading center), PDR (as confirmed by the central reading center), or ASNV (as confirmed by the investigator) that requires treatment will continue participation in the study. The central reading center must confirm progression to CI-DME or PDR before the investigator initiates treatment.

Specific safety, tolerability, and efficacy assessments will occur at every visit as presented in the schedule of assessments in [Section 3.2](#). Blood samples for the assessment of PK, biomarkers, and pharmacogenomics will be obtained at various time points during the study as shown in the schedule of assessments ([Section 3.2](#)). Participation in the pharmacogenomic and aqueous humor sampling is optional and is not required for participation in the study; for those participants electing to participate in either of these optional portions, blood samples for the assessment of pharmacogenomics and aqueous humor samples will be collected.

The study will be conducted at approximately 25 sites in the United States. Approximately 80 participants are planned for enrollment to provide data for 69 completed participants (ie, participants who complete the 24-week assessments). The overall duration of the study, inclusive of recruitment, is approximately 14 months from study initiation (ie, following consent of first participant) to study completion (ie, last participant, last visit [LPLV]). The participation period for each participant is approximately 32 weeks, inclusive of a 4-week Screening period, 24-week Treatment period, and a 4-week Follow-up period.

A study flow diagram is provided in [Figure 1](#).

**Figure 1** Study Flow Diagram

### 3.2 Schedule of Assessments

For the complete schedule of assessments, refer to Section 15 (Schedule of Events) and Section 17.4 (Pharmacokinetic, Biomarker, Pharmacogenomic, and Flow Cytometry/CBC Sampling) of the clinical study protocol.

### 3.3 Treatment

### ***3.3.1 Treatment Administered***

Study treatment consists of AKST4290 or matched placebo. AKST4290 is a film-coated pink, oblong tablet manufactured by Alkahest, Inc., with a unit strength of 400 mg and is packaged in “foil-foil” blister packets. Each packet will include 14 tablets.

Study drug will be self-administered orally b.i.d., approximately 12 hours apart. AKST4290 will be administered as a total daily dose of 800 mg (400 mg b.i.d.). Matching placebo will be self-administered orally b.i.d. following the same dosing instructions as AKST4290.

Participants will receive training on study drug administration prior to initial study drug administration at Visit 2. Study drug will be self-administered in the clinic under the supervision of study personnel during every in-clinic visit of the Treatment Period (Visits 2-8) after any pre-dose assessments (including PK sample collection), and then self-administered at home between study visits.

When study drug is dispensed, participants will receive a total of 5 packets, which represents a 5-week supply (4 weeks of treatment plus an additional week). Study drug accountability will be assessed by packet.

### ***3.3.2 Method of Assigning Subjects to Treatment Groups***

To minimize the potential bias at the time of randomization, the study will be double-masked and randomized in a 2:1 ratio (active 400 mg b.i.d.: placebo b.i.d.) based on a block randomization schema. The randomization will be stratified by DRSS category at baseline (moderately severe NPDR [DRSS level 47] to severe NPDR [DRSS level 53]). The randomization codes will be generated by a statistician who is not involved in the study other than generation and maintenance of the randomization codes.

### ***3.3.3 Masking Procedures***

Maintenance and assignment of the randomization codes will be by a web-based randomization system. The study mask for either AKST4290 versus placebo can be broken for safety reasons if the information is required for the management of serious adverse events (SAEs), severe adverse events (AEs), or pregnancies. Before breaking the mask, every attempt should be made to discuss the need with the Sponsor program physician, or designee. When some degree of unmasking must occur, this should be limited to the fewest number of people on a need-to-know basis.

The investigator can obtain the AKST4290 or placebo treatment allocation for their participant through the web-based randomization system or by contacting the interactive response technology vendor.

## **3.4 Efficacy and Safety Variables**

### **3.4.1 Efficacy Variables**

#### **3.4.1.1 Primary Efficacy Variable**

The primary efficacy endpoint is the proportion of participants with a  $\geq$  3-step improvement from baseline on the DRSS score as compared with Week 24.

Progression of diabetic retinopathy (DR) is measured in discrete steps as described by the DRSS ([ETDRS 1991b](#), [Staurenghi 2018](#)). The DRSS divides DR into 13 levels ranging from the absence of retinopathy to severe retinopathy (see Table 1 of the clinical study protocol) and is used to describe overall DR severity as well as the change in severity over time.

After pupillary dilation, the retina of both eyes will be imaged by fundus photography (FP) and fluorescein angiography (FA). Both eyes will be investigated by a trained technician and evaluated by the investigator. Findings from FP and FA, as provided by the central reading center, will be used to determine the DRSS score for each participant. Fundus photography will be performed at Visit 1 (Screening), each of the in-clinic study visits in the Treatment Period, Visit 2 (Baseline) through Visit 8 (End of Treatment [EOT]/Early Termination [ET]), and Visit 9 (End of Study [EOS]); fluorescein angiography will be completed at Visits 1 (Screening), Visit 5, and Visit 8 (EOT/ ET). Fundus photography and FA must be performed once a participant has been diagnosed with CI-DME or PDR, and before rescue treatment is given. Given the abbreviated scope of the SAP due to the study status, the DRSS level determined for each eye will be presented as assigned by the central reading center and a single bilateral severity level will not be derived to determine step-wise improvements.

#### **3.4.1.2 Secondary Efficacy Variables**

Secondary efficacy endpoints include the following:

- The proportion of participants with a  $\geq$  2-step improvement from Baseline on the DRSS score as compared with Week 24.
- The proportion of participants progressing to the following vision-threatening complications that require treatment: CI-DME, PDR, and/or ASNV as assessed by spectral domain optical coherence tomography (SD-OCT), FP, and FA, as appropriate. The central reading center must confirm progression to CI-DME and PDR before treatment is initiated; progression to ASNV, and subsequent treatment, does not require photo documentation.
- Time to the following vision-threatening event(s) that require treatment: CI-DME, PDR, and/or ASNV.
- Effect of AKST4290 on diabetic kidney disease as assessed by changes in clinical laboratory values over time (eg, estimated glomerular filtration rate [eGFR], urine albumin to creatinine ratio [UACR]).
- Change from Baseline over time in the WPAI-GH questionnaire.

The DRSS score as derived from FP and FA findings, is described in [Section 3.4.1.1](#).

Assessment of vision-threatening complications including CI-DME, PDR and ASNV is based on SD-OCT, FP, and FA as appropriate. Evaluation of FP and FA are described in [Section 3.4.1.1](#). The retinal layers of both eyes will be visualized, and thickness measured by SD-OCT at Visit 1 (Screening), each in-clinic study visit of the Treatment Period, and Visit 9 (EOS). Both eyes will be investigated by a trained technician using only specified SD-OCT equipment. A central reading center will be responsible for assessing all SD-OCT, OCT-A, FP, VF, and FA images to confirm study eligibility and progression to PDR and/or CI-DME and will provide the imaging data for inclusion in the database for the evaluation of efficacy and safety. Progression to vision-threatening complications is collected directly on the electronic case report form (eCRF) including whether or not the complication required treatment. Subjects who progress to a vision-threatening complication and treatment is indicated by a “Yes” response to the question “Was the vision-threatening complication treated?” will be considered to have a vision-threatening complication that required treatment.

Collection of laboratory parameters, including eGFR and UACR, is described in [Section 3.4.2.2](#).

The WPAI-GH V2.0 is a 6-question survey used to assess the effects of a participant’s health problems (ie, physical or emotional problems or symptoms) on their ability to work and perform regular activities during the past seven days. The WPAI-GH will be performed at Visit 2 (Baseline), Visit 4, Visit 6, and Visit 8 (EOT/ET).

The WPAI-GH questions will be analyzed as impairment percentages, in which higher percentages indicate greater impairment and less productivity ([Reilly 1993](#)). The following parameters will be calculated (multiply scores by 100 to express in percentages):

- Percent of work time missed due to health: Q2 divided by (Q2 plus Q4)
- Percent of impairment while working due to health: Q5 divided by 10
- Percent of overall work impairment due to health: Q2 divided by (Q2 plus Q4) plus [(1 - (Q2 divided by (Q2 plus Q4 ))) multiplied by (Q5 divided by 10)]
- Percent of activity impairment due to health: Q6 divided by 10

A subject must have a response provided for all questions used in the percentage for the impairment percentage parameter to be calculated.

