17.5. Work Productivity and Activity Impairment Questionnaire: General Health

The WPAI-GH V2.0 is a 6-question survey used to assess the effects of a participant's health problems (i.e., physical or emotional problems or symptoms) on their ability to work and perform regular activities during the past 7 days. In clinical trials, the WPAI-GH has been used to compare work impairments between treatment groups in participants with varying levels of disease severity (Zhang 2010). The questionnaire below is provided as an EXAMPLE ONLY. The actual assessment and instructions for administration and scoring will be included in a rater reference manual or equivalent.

The following questions ask about the effect of your health problems on your ability to work and perform regular activities. By health problems we mean any physical or emotional problem or symptom. *Please fill in the blanks or circle a number, as indicated.*

1. Are you currently employed (working for pay)? NO YES
If NO, check "NO" and skip to question 6.

The next questions are about the **past seven days**, not including today.

2. During the past seven days, how many hours did you miss from work because of your health problems? *Include hours you missed on sick days, times you went in late, left early, etc., because of your health problems. Do not include time you missed to participate in this study.*

HOURS

3. During the past seven days, how many hours did you miss from work because of any other reason, such as vacation, holidays, time off to participate in this study?

HOURS

[figure not shown]
4. During the past seven days, how many hours did you actually work?

HOURS *(If "0", skip to question 6.)*

5. During the past seven days, how much did your health problems affect your productivity while you were working?

Think about days you were limited in the amount or kind of work you could do, days you accomplished less than you would like, or days you could not do your work as carefully as usual. If health problems affected your work only a little, choose a low number. Choose a high number if health problems affected your work a great deal.

Consider only how much health problems affected productivity while you were working.

[figure not shown]

CIRCLE A NUMBER

6. During the past seven days, how much did your health problems affect your ability to do your regular daily activities, other than work at a job?

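### SAP 3.4.1.2 leaves overall work impairment (WPAI-GH) missing for a participant who missed all work for health, although its own formula gives 100%

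*SAP*

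**What the plan says.** The WPAI-GH is a secondary efficacy endpoint: "Change from Baseline over time in the WPAI-GH questionnaire" (SAP 3.4.1.2; likewise Protocol 4.2.2). SAP 3.4.1.2 defines four impairment percentages. Two of them matter here:

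- "Percent of work time missed due to health: Q2 divided by (Q2 plus Q4"), which uses Q2 (hours missed for health) and Q4 (hours worked).
- "Percent of overall work impairment due to health: Q2 divided by (Q2 plus Q4) plus" a second term, the remaining fraction of work time "multiplied by (Q5 divided by 10"). This one also uses Q5 (effect of health on productivity while working).

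The other two are impairment while working (Q5 only) and activity impairment (Q6 only). One missing-item rule covers all four: "A subject must have a response provided for all questions used in the percentage for the impairment percentage parameter to be calculated". No exception is stated.

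The form in Protocol 17.5 asks at question 4: "During the past seven days, how many hours did you actually work"? A participant who answers zero is told to "skip to question 6", so Q5 is never put to that person. Protocol 17.5 labels this form an example and leaves administration and scoring instructions to a rater manual.

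SAP 4.3.3 still plans to list both the raw answers and the derived percentages. SAP sections 1, 4.1 and 4.6 restrict reporting to listings after early termination.

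**The concern.** The all-items rule makes sense when an answer is absent and the result cannot be known. Here the answer is absent because the form does not ask for it, and the result does not depend on it. The blank also falls at the worst end of the scale: near-total absence from work is scored, total absence is not.

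For the SAP as it stands, what is at stake is the correctness of one derived value in a listing. In a full-size analysis more would follow. Missingness would be determined by the outcome itself. A blank at Baseline would also remove that participant's change from Baseline in this parameter at every later visit.

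**Working it through.** **Inputs.** The formulas and the missing-item rule are from SAP 3.4.1.2; the routing is from the example form in Protocol 17.5. The plan states no figure that could be reproduced. The responses below are chosen to exercise the rule and are not trial data.

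**Formula.** Overall work impairment = 100 x { Q2/(Q2+Q4) + [1 - Q2/(Q2+Q4)] x Q5/10 }.

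**Total absence for health: Q2 = 40, Q4 = 0, Q5 not asked, Q6 = 9.**

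- Work time missed = 40/(40+0) = 100%.
- Impairment while working: missing. This is right, because no work was done.
- Overall work impairment under the SAP rule: missing, because Q5 has no response.
- Overall work impairment by the formula: 40/40 + (1 - 40/40) x Q5/10 = 1 + 0 x Q5/10 = 100%. Evaluating it at every Q5 from 0 to 10 gives 100% each time.
- Activity impairment = 9/10 = 90%.

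The same holds for any Q2 > 0. With Q2 = 1 and Q4 = 0 the first term is again 1 and the second again 0.

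**Neighbouring cases, which are kept.**

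| Q2 | Q4 | Q5 | Work time missed | Overall, SAP rule | Overall, formula |
|---|---|---|---|---|---|
| 20 | 20 | 5 | 50% | 75% | 75% |
| 36 | 4 | 8 | 90% | 98% | 98% |
| 39 | 1 | 10 | 97.5% | 100% | 100% |
| 40 | 0 | not asked | 100% | missing | 100% |

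**Undefined case.** With Q2 = 0 and Q4 = 0 (no work, for reasons other than health) the ratio is 0/0. Missing is correct for both work time missed and overall work impairment. The all-items rule does not cover this for work time missed, because Q2 and Q4 have both been answered.

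**What reuse in an analysis would do (assumed figures; the documents give none).** Let a fraction f of employed participants be fully absent for health, and let the others have mean m. The mean with the 100% scores included is 100f + m(1 - f). Under the rule it is m, so it is too low by f(100 - m). With m = 20%:

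- f = 2%: 0.02 x 80 = 1.6 points (21.6% becomes 20%).
- f = 5%: 0.05 x 80 = 4.0 points (24% becomes 20%).
- f = 10%: 0.10 x 80 = 8.0 points (28% becomes 20%).

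If the arms had f = 2% and f = 10% and were otherwise equal, a difference of 28.0 - 21.6 = 6.4 points in this parameter would show as 0. The current SAP makes no such comparison.

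**The case against.** The strongest objection is that nothing in this study turns on the gap. Three participants were randomized and on drug when investigators were told to stop, and their employment status is not given. SAP 4.1, 4.3 and 4.6 provide listings only, and the mixed model that Protocol 10.4.4 planned for the WPAI-GH is not carried over. Because SAP 4.3.3 lists the raw answers, a reader who sees Q2 > 0 and Q4 = 0 can supply the 100%. All of this stands, and it is why the point is minor.

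A second objection is that the routing comes from an example form. The rater manual, or the published scoring source that the SAP cites, may deal with a skipped Q5; neither is available here. That lowers the certainty that a blank would appear in practice. It does not repair the SAP, which states its own rule without an exception.

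A third is that even under the full design the WPAI-GH carried little weight. It is listed as secondary, but Protocol 10.4.4 places its analysis among the exploratory endpoints, for which Protocol 10.4.6 plans no formal testing. This too is fair.

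Against these, the shortened SAP drops other derivations, such as the bilateral DRSS level and the BCVA area under the curve, and deliberately keeps this one. A derivation that is kept should return the value that its formula determines.

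**Conclusion.** The point holds as a minor scoring error. For an employed participant with Q2 > 0 and Q4 = 0, SAP 3.4.1.2 as written leaves overall work impairment blank where its own formula gives 100%. The listing would show that blank beside 100% work time missed. This assumes that the form in use routes past Q5 as the example does, and that the rule is programmed literally.

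A reader might infer three stronger things that the documents do not support:

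- **That the most impaired participants are dropped.** No participant is dropped. One of four percentages is blank; work time missed and activity impairment are derived, and impairment while working is rightly missing.
- **That reported means are biased low.** The current SAP computes no means.
- **That a drug effect on complete work absence would be lost.** The SAP makes no treatment comparison. Even in a full analysis, such an effect would still appear in work time missed, which does not use Q5.

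Outcome-dependent missingness becomes a real concern only if this rule is reused in an analysis such as the repeated-measures model in Protocol 10.4.4.

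**What to change.** Add to SAP 3.4.1.2, directly after the all-items rule: if Q4 = 0 and Q2 > 0, overall work impairment is set to 100% and Q5 is not required; if Q2 + Q4 = 0, work time missed and overall work impairment are set to missing. Leave the rule unchanged for the other parameters, and check the wording against the scoring instructions in the rater manual.

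The cost is one sentence in the SAP and one condition in the derivation program. No new data are needed, and no other listed value changes.
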